3 INCLUSION AND EXCLUSION CRITERIA

3.1 Inclusion Criteria:

To be included in this study, participants must meet the following criteria:

1. Recurrent and/or metastatic unresectable colorectal cancer with hepatic metastases.
2. Hepatic metastases present which are amenable to biopsy.
3. Prior treatment with, contra-indication to or refusal of a fluoropyrimidine, irinotecan, oxaliplatin and an anti-EGFR targeted therapy (if RAS wt), as well as a PD-1 or PD-L1 targeted drug if MSI-H/dMMR.
4. No chemotherapy, radiotherapy, major surgery, or biologic therapy within 3 weeks of protocol treatment.
5. An ECOG performance status of 0, 1, or 2. Refer to Appendix C.
6. Have measurable disease per RECIST 1.1 criteria present.
7. Ability to swallow and retain oral medications.
8. Participants of child-bearing potential must agree to use adequate contraceptive methods (e.g., hormonal or barrier method of birth control; abstinence) prior to study entry. Should a woman become pregnant or suspect she is pregnant while she or her partner is participating in this study, she should inform her treating physician immediately.
9. Age equal to 18 years or older.
10. Must have normal organ and marrow function as defined below:
 - Platelet \geq 75,000/ μ L
 - Hemoglobin \geq 9 g/dL
 - Hematocrit \geq 27%
 - Absolute Neutrophil Count (ANC) \geq 1500/ μ L
 - Creatinine \leq institutional upper limit of normal (ULN)

OR

- Creatinine clearance \geq 50 mL/min for patients with creatinine levels greater than ULN (refer to Appendix I for Cockcroft-Gault Equation)
- Total bilirubin \leq 1.5 X institutional ULN or for patients with known Gilbert's Syndrome total bilirubin \leq 3 x ULN
- AST (SGOT) and ALT(SGPT) \leq 2.5 X institutional ULN
- Plasma amylase and lipase \leq 1.5 X institutional ULN.

PROTOCOL TITLE: Phase 2A Study Evaluating a Chemokine-Modulatory Regimen in Patients with Colorectal Cancer Metastatic to the Liver

11. Participant or legal representative must understand the investigational nature of this study and sign an Independent Ethics Committee/Institutional Review Board approved written informed consent form prior to receiving any study related procedure.

Please refer to Appendix D for the Investigator Study Eligibility Verification Form: Inclusion Criteria.

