9.2 Treatment Phase

A total of three weeks of therapy will be planned. Serial liver biopsies will be obtained, with the first performed prior to initiating therapy and the second performed on Day 20 (\pm 2 days). Following completion of the 3 consecutive weeks of treatment, the study treatment period will conclude. In order to secondarily assess clinical benefit, repeat CT imaging will be assessed at day 46 (\pm 3 days). If a patient completes therapy and a decision is made to pursue a further alternate treatment, the subject will come off study; however, in this circumstance, assessment of the next clinical staging study will be requested for determination of RECIST parameters.

Schema

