11.1.6 Follow-up (patients will be followed for 12 months after EOT visit)

- Survival status (phone contact/chart review is acceptable)
- CT scan and/or MRI: to be performed at day 46 (\pm 3 days). If reassessment scan shows stable disease/response, patients will continue in follow-up with CT imaging every 8 weeks until progression, clinical deterioration or withdrawal from study. If in the clinical judgment of the treating team, it is in the best interest of the patient to pursue another therapeutic option, the patient will come off study and CT imaging will be obtained only as SOC/protocol. In this instance, review of the subsequent disease assessment study will be requested for determination of RECIST parameters.

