19.3 Proposed Data Analysis

Primary Analysis: The *primary objective* is to determine the impact of a chemokine-modulatory regimen on the immune microenvironment of colorectal liver metastases. The *primary endpoint* is the change in TILs, as measured by CD8= transcript, which is treated as a continuous variable.

The TILs will be summarized by time-point (pre-/post-treatment) using the mean, median, standard deviation; and graphically using dot-plots. A 90% confidence interval for the mean change in TILs will be obtained using standard methods. Using a one-sided permutation paired t-test, the following hypotheses about the change in TILs will be evaluated:

$$H_0: \mu_d \leq 0 \text{ versus } H_A: \mu_d > 0,$$

where μ_d is the true change in TILs (post-treatment – pre-treatment).

This analysis will be limited to subjects who are considered evaluable for efficacy. Therefore the recommended sample size for efficacy is 12 *evaluable subjects*.

Secondary Analysis: The secondary objectives are to evaluate the clinical outcome of objective response and safety of the proposed therapy. The responses (based on RECIST v1.1 criteria) will be treated as binary data and summarized using frequencies and relative frequencies; with the objective response rate (ORR) estimated using a 90% confidence interval obtained using Jeffrey’s prior method. The safety analysis is described in Section 9.4.

Exploratory Analyses: The exploratory objectives are to evaluate the clinical outcomes of overall survival (OS) and progression-free survival (PFS). The OS and PFS will be treated as bivariate time-to-event data and will be summarized using standard Kaplan-Meier methods. OS will be defined as the time from the start of treatment until death due to any cause or last follow-up. PFS will be defined as the time from the start of treatment until disease progression (defined by RECIST 1.1) or last-follow-up.

PROTOCOL TITLE: Phase 2A Study Evaluating a Chemokine-Modulatory Regimen in Patients with Colorectal Cancer Metastatic to the Liver

Interim Analysis: As part of amendment #8, an interim analysis will be utilized to examine whether refinement of patient selection (i.e. earlier line) and tumor selection (i.e. selection of lesion and number of tumor cores) will improve: 1) the intra-subject variability observed in the first patients (likely due to choice of lesion and abundance of necrotic tissue), and efficacy with respect to the primary end-point (change in TILs).

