Appendix G

RECIST 1.1 Criteria

Objective Tumor Response

All protocol-defined imaging studies must be performed at the investigative site or sponsor-approved facility using protocol-defined parameters. The same method of assessment and the same technique should be used to characterize each identified and reported lesion at baseline and during follow-up. RECIST 1.1 will be used to assess objective tumor response.

Target Lesions

All measurable lesions up to a maximum of 2 lesions per organ and 5 lesions in total, representative of all involved organs, will be identified as target lesions and recorded and measured at baseline. Target lesions will be selected on the basis of their size. Lesions with the longest diameter (short axis for lymph nodes) and are ≥ 10 mm (CT and MRI), ≥ 15 mm lymph nodes, > 20 mm CXR and are for accurate repetitive measurements (either by imaging techniques or clinically) will be chosen. A sum of the longest diameter (short axis for lymph nodes) of all target lesions will be calculated and reported as the baseline sum diameters. This will be used as reference to further characterize the objective tumor response of the measurable dimension of the disease.

- **Complete Response (CR):** Disappearance of all target lesions. Any lymph nodes must have a reduction in short axis to < 10 mm. Changes in tumor measurements must be confirmed by repeat studies performed no less than 6 weeks after the criteria for response are first met.
- **Partial Response (PR):** At least a 30% decrease in the sum of diameters of target lesions, taking as reference the baseline sum diameters. Changes in tumor measurements must be confirmed by repeat studies performed no less than 6 weeks after the criteria for response are first met.
- **Progressive Disease (PD):** At least a 20% increase in the sum of diameters of target lesions, taking as references the smallest sum on study (this includes the baseline sum if that is the smallest on study). In addition to the relative increase of 20%, the sum must also demonstrate an absolute increase of at least 5 mm. The appearance of one or more new lesions is also considered progression.
- **Stable Disease (SD):** Neither a sufficient shrinkage to qualify for PR nor sufficient increase to qualify for PD, taking as reference the smallest sum diameter while on study. Participants having a documented response with no confirmation of the response will be listed with stable disease.

Non-Target Lesions

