¹ Non-CR/non-PD is preferred over SD for non-target disease since SD is used as endpoint for assessment of efficacy in trials so to assign this category when no lesions can be measured is not advised.

The best overall response is the best response recorded from the start of study treatment until disease progression, taking into account any requirement for confirmation. In general, the

Date 102920

PROTOCOL TITLE: Phase 2A Study Evaluating a Chemokine-Modulatory Regimen in Patients with Colorectal Cancer Metastatic to the Liver

participant's best response assignment will depend on the achievement of both measurement and confirmation criteria and will be determined by combining the participant's status of target lesions, non-target lesions, and new lesions.

- **Symptomatic Deterioration:** Participants with global deterioration of health status requiring discontinuation of treatment without objective evidence of disease progression at that time, and not related to study treatment or other medical conditions should be reported as progressive disease due to "symptomatic deterioration." Every effort should be made to document objective progression even after discontinuation of treatment due to symptomatic deterioration. Symptomatic deterioration that may lead to discontinuation of treatment include, but is not limited to, symptoms such as:
 - Weight loss > 10% of body weight.
 - Worsening of disease-related symptoms (e.g., worsening dyspnea, increasing pain/increasing requirement for narcotic analgesics).
 - Decline in performance status of > 1 level on ECOG scale.

Confirmation Measurement

If Day 46 CT scan demonstrates stable disease/response, patients will continue in follow-up with CT imaging every 8 weeks until progression, clinical deterioration or withdrawal from study.

Guidelines for Evaluation of Measurable Disease

All measurements should be taken and recorded in metric notation. All baseline evaluations should be performed as closely as possible to the beginning of treatment and never more than 4 weeks before the beginning of the treatment.

The same method of assessment and the same technique should be used to characterize each identified and reported lesion at baseline and during follow-up. Imaging-based evaluation is preferred to evaluation by clinical examination unless the lesion(s) being followed cannot be imaged but are assessable by clinical exam.

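### No rule ends best overall response or PFS at new anticancer therapy, so the next treatment's effect can be credited to the regimen: directly for PFS and stable disease, only in part for ORR

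*Combined protocol and SAP*

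**What the plan says.** **Scans after a switch.** Under section 9.2, a patient who completes therapy and then pursues an alternate treatment comes off study, but "in this circumstance, assessment of the next clinical staging study will be requested for determination of RECIST parameters". Section 11.1.6 says the same of follow-up: "review of the subsequent disease assessment study will be requested for determination of RECIST parameters". Section 9.3 adds that further CT imaging is then done only per standard of care or protocol, and that the new treatment is recorded in the database.

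**Response.** Appendix G states: "The best overall response is the best response recorded from the start of study treatment until disease progression". The sentence goes on to make this subject to any confirmation requirement. Appendix G also says: "Participants having a documented response with no confirmation of the response will be listed with stable disease". Section 19.3 gives the analysis: "The responses (based on RECIST v1.1 criteria) will be treated as binary data", with a 90% Jeffreys interval.

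**PFS.** Section 19.3: "PFS will be defined as the time from the start of treatment until disease progression (defined by RECIST 1.1) or last-follow-up".

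**When a switch is possible.** Section 10.3 bars other anticancer therapy only during active treatment. Dosing ends on Day 17 and the first response scan is on Day 46 (± 3 days). Inclusion criterion 3 accepts "Prior treatment with, contra-indication to or refusal of a fluoropyrimidine, irinotecan, oxaliplatin" among its conditions, so a patient who declined a standard agent can be enrolled.

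**Safety, by contrast.** Section 17.3 closes the routine SAE reporting window at 30 days after the last intervention or at the start of a new treatment, whichever is earlier. Sections 17.2 and 17.4 also name the start of new treatment as an end point. The efficacy sections have no counterpart.

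**The concern.** The secondary objective is to estimate the response rate of this regimen, and an exploratory objective is to estimate its median PFS. The trial has one arm, so no control group removes the contribution of a later treatment. Only a cut-off at new therapy can do that.

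The plan has no such cut-off, and it actively asks for a RECIST reading after the patient has left for something else. For a patient who switches before Day 46, that reading may be the only post-baseline assessment. If the next treatment has any activity, the bias favours the regimen.

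**Working it through.** **1. The plan's own figure.** The only power statement concerns the primary endpoint (section 19.2): n = 12, shift 0.77 SD, one-sided alpha 0.1. For the paired t-test, df = 11, critical value 1.363 and noncentrality 0.77 × √12 = 2.667, which gives power 0.900. The stated 90% reproduces. It rests on the paired biopsies, so nothing below alters it. ORR and PFS have no stated precision or power.

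**2. Time open for a switch.** From last dose to first response scan is 46 − 17 = 29 days (26 to 32 with the ± 3-day window).

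**3. Each endpoint against the text, for a patient who switches without progression.**

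| Endpoint | Ends at new therapy? | Other safeguard | Exposure |
|---|---|---|---|
| PFS (19.3) | No | None stated | Direct |
| Stable disease as best response (Appendix G) | No | None stated | Direct |
| CR or PR, hence ORR (Appendix G, 19.3) | No | Confirmation required; unconfirmed is listed as stable disease | Partial |

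**4. Routes to a misattributed response.** Sections 9.2 and 11.1.6 request one study after the switch. A first response on that study alone is listed as stable disease, so it does not reach ORR. Two routes remain:
- A response on Day 46 is followed by a switch and confirmed on the new therapy. Confirmation falls no earlier than Day 46 + 42 = Day 88 under Appendix G (6 weeks), or Day 46 + 28 = Day 74 under section 16.1 (4 weeks). The scheduled 8-week scan is at Day 46 + 56 = Day 102.
- Two or more later standard-of-care scans supply both the response and its confirmation.

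**5. Size for ORR, illustration only.** The 90% Jeffreys interval takes the 5th and 95th percentiles of Beta(x + 0.5, n − x + 0.5), with the lower limit set to 0 at x = 0. Denominators are assumptions: 15 is the approximate planned enrolment, and 12 (the primary evaluable number) shows the sensitivity.

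| Confirmed responses | n = 15 | n = 12 |
|---|---|---|
| 0 | 0% (0 to 11.8%) | 0% (0 to 14.5%) |
| 1 | 6.7% (1.2% to 23.3%) | 8.3% (1.5% to 28.3%) |

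Each misattributed confirmed response adds 1/15 = 6.7 percentage points at n = 15.

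**6. Size for PFS, illustration only.** None of these inputs is in the documents: exponential PFS with true median m; a fraction f of patients who switch at day 30 if progression-free; hazard ratio h on the next treatment; progression observed continuously. With λ = ln 2 / m, for t > 30 and no cut-off:

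S(t) = (1 − f)·exp(−λt) + f·exp(−30λ)·exp(−λh(t − 30)).

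Solving S(t) = 0.5 for f from 0.2 to 0.4 and h from 0.7 to 0.5:

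| True median (days) | Median without cut-off (days) |
|---|---|
| 46 | 47 to 50 |
| 60 | 62 to 68 |
| 90 | 94 to 107 |

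The lengthening is about 1 to 17 days. Censoring at the switch recovers the true median in this model, but only because switching is unrelated to prognosis there. Real scans every 8 weeks would make the observed shift coarser.

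**The case against.** - **Confirmation protects ORR.** A reader might infer that any partial response on the next drug counts toward ORR. Appendix G does not support that, since a first response on the single requested scan is listed as stable disease. This objection stands and limits the ORR point to the two routes in the working. It does nothing for PFS or for stable disease as best response.
- **The requested scan may precede the new drug.** A reader might assume that it is usually taken on the new therapy. The documents do not say; it could be a restaging scan before the first dose. Also, a patient who switches after Day 46 already has a scheduled pre-switch scan. So the effect can be misattributed, but not necessarily.
- **Last follow-up might mean the off-study date.** That reading would end PFS at the switch. The text does not define the term, and the request for a later RECIST reading points the other way. The wording is ambiguous at best.
- **Censoring at new therapy has its own weakness.** Under section 9.3 the switch follows the treating team's clinical judgement, so censoring may be informative. A patient who switches before any post-baseline scan would add almost nothing to PFS. This stands, and it is why a sensitivity analysis belongs in the fix.
- **The endpoints are not decisive.** ORR is secondary and PFS exploratory. Both are estimated without a test or threshold, and new treatment is already recorded. This stands on severity. It does not remove the need to state the rule before the data are seen.

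**Conclusion.** The gap is real. The plan asks for RECIST readings after patients leave for another treatment, and it has no rule ending best overall response or PFS at that point. PFS and stable disease as best response are directly open to the next treatment's effect; ORR is open only in part.

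The sizes are illustrations. One misattributed confirmed response would move ORR from 0/15 to 1/15 and the 90% upper limit from 11.8% to 23.3%. Median PFS could lengthen by about 1 to 17 days under the assumed inputs. The number of switchers, the activity of their next treatment and the exact ORR denominator are not given. Inclusion criterion 3 shows that some patients could have untried options, but not how many.

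A reader might also infer that the trial's main result is compromised. It is not: the primary biopsy endpoint, its power and OS do not depend on these scans. Severity is moderate, and the change is a cheap improvement rather than a condition for proceeding.

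**What to change.** Amend sections 9.2, 11.1.6 and 19.3 and Appendix G so that they state one rule:

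1. Only assessments made before the first dose of any new anticancer therapy count toward best overall response, confirmatory scans included.
2. Treated patients who switch without a qualifying scan stay in the ORR denominator as non-responders. This needs saying because section 19.2 limits the secondary cohort to treated patients followed for clinical outcomes, which could be read as dropping them.
3. PFS is censored at the last adequate scan before new therapy. A sensitivity analysis follows patients through new therapy, because switching may be informative.
4. Scans after new therapy are listed descriptively.
5. The minimum confirmation interval is reconciled between section 16.1 (not less than 4 weeks) and Appendix G (no less than 6 weeks).

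**Cost.** Wording only. Section 9.3 already captures new-treatment information; the start date must be part of it for the cut-off to be applied. ORR may come out slightly lower, and PFS loses some follow-up. Sample size, the primary analysis and OS do not change.

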9.3 Follow-up Phase

Patients will be seen for an end of treatment visit to review adverse events, clinical outcome of therapy. If stable disease/response is demonstrated during repeat CT imaging, patients will continue in follow-up with CT imaging every 8 weeks until progression, clinical deterioration or withdrawal from the study. If in the clinical judgement of the treating team, it is in the best interest of the patient to pursue another therapeutic option, the patient will come off study and CT imaging will be obtained only as per SOC/protocol. 12 months of survival follow-up will be pursued by chart audit or if necessary phone contact. If the patient comes off study during the follow-up period to start a new treatment, the new treatment information will be captured in the database.

10 TREATMENT

10.1 Dosing and Administration

10.1.1 Chemokine modulating regimen

For dosing, refer to Table 1. The chemokine modulating regimen will be administered on an outpatient basis at Roswell Park Cancer Institute over 3 consecutive days, every week x 3 weeks (Days 1, 2, 3, 8, 9, 10, 15, 16, 17) in the following order:

- Pretreatment: 500 mL Normal saline IV over 60 minutes
- Pre-meds: Acetaminophen (Tylenol) 650 mg by mouth x 1 dose; Prochlorperazine (Compazine) 10 mg by mouth x 1 dose – administered 30 minutes (\pm 5 minutes) after starting pre-treatment hydration

PROTOCOL TITLE: Phase 2A Study Evaluating a Chemokine-Modulatory Regimen in Patients with Colorectal Cancer Metastatic to the Liver

- Celecoxib: 200 mg orally, administered along with pre-meds
- Interferon Alpha-2b : (20 million units/M²) IV over 20 minutes
- Rintatolimod: 200 mg IV, initial administration should begin at a slow rate of infusion (approximately 20 cc/ hour) and increase to 40 cc/ hour after 30 minutes. Tubing should be flushed with 30 to 50 mL of normal saline solution upon completion. Administration will be followed by 1 hour of observation and vital signs at 30 and 60 minutes post infusion (\pm 5 minutes)
- Celecoxib: 200 mg orally to be taken by the patient at home approximately 12 hours following the initial dose.

Pretreatment and pre-meds listed above are recommendations and may be modified based upon institutional SOC requirements and at the discretion of the investigator. Treatment is intended for an outpatient setting. However, at the investigator's/physician's discretion, the participant may receive treatment as an inpatient, if deemed necessary.

Each 3 day treatment will be initiated after interval history and physical examination is performed and once the relevant laboratory studies have been confirmed to be within clinically acceptable ranges, specifically: ANC \geq 1000/mm³, total bilirubin \leq 1.5 x ULN or \leq 3 x ULN (for patients with Gilbert's Syndrome), AST and ALT $<$ 3 x ULN (or $<$ 150% of values at baseline). Treatment may be delayed up to 3 weeks to allow for resolution of any intercurrent illness or for logistical reasons. Delays beyond 3 weeks will require discussion with the study PI to review appropriateness of continuing therapy on study.

10.2 Dose Modification

The following dose modification rules will be used with respect to potential toxicity. Toxicity will be assessed according to the NCI Common Terminology Criteria for Adverse Events Version 5.0 (CTCAE v5.0).

Therapy will be immediately discontinued for any grade IV treatment-related toxicity that becomes apparent. The exception to this is for grade 4 neutropenia of $<$ 7 days duration. Study treatment will be reinitiated for any grade treatment-related III toxicity pending the reversal of such toxicity after withholding treatment (i.e. the toxicity resolves to the subject's baseline level). In the event of any adverse effect, appropriate medical treatment will be instituted and study treatment will be discontinued if the above toxicity remains.

PROTOCOL TITLE: Phase 2A Study Evaluating a Chemokine-Modulatory Regimen in Patients with Colorectal Cancer Metastatic to the Liver

Table2. Treatment Related Toxicity Management

Treatment-related AEs	Toxicity grade or conditions (CTCAE5.0)	Action taken for Interferon Alpha-2b	Action taken for Rintatolimod	Action taken for Celecoxib	Additional actions
Chills/Fever	Grade 3	None	None	None	Consider additional acetaminophen dosing, supportive care
Pancreatitis	Grade 3	Hold Decreased future doses by 50%	Hold	Hold	Supportive measures as clinically indicated
AST / ALT elevation or Increased bilirubin	Grade 3	Hold until improved to grade 1; Decrease future doses by 50%	Hold	Hold	Advise evaluation for other possible etiologies; consider imaging
Vomiting	Grade 3	Hold until resolved to grade 1; Decrease future doses by 50%	Hold	Hold	
Neuropathy	Grade 2 or greater	Hold until decreased to patient's baseline; Decrease future doses by 50%	None	None	
Depression or other clinically relevant mood disorder	Grade 3	Permanently discontinue; appropriate supportive care/intervention	None	None	
Neutropenia	Grade 3 or greater	Hold until ANC > 1000; Decrease future doses by 50%	Hold	Hold	
Hemorrhage	Grade 2 or greater	None	None	Permanently discontinue	
Myocardial infarction or other arterial thrombotic event	Grade 2 or greater	None	None	Permanently discontinue	

PROTOCOL TITLE: Phase 2A Study Evaluating a Chemokine-Modulatory Regimen in Patients with Colorectal Cancer Metastatic to the Liver

Treatment-related AEs	Toxicity grade or conditions (CTCAE5.0)	Action taken for Interferon Alpha-2b	Action taken for Rintatolimod	Action taken for Celecoxib	Additional actions
All other clinically significant AEs ¹	Intolerable Grade 2 or Grade 3	Hold therapy until resolved; reduce future doses by 50%	Hold therapy until resolved; reduce future doses by 50%	Hold therapy until resolved	
	Grade 4	Permanently Discontinue	Permanently Discontinue	Permanently Discontinue	
1. Holding of any therapies here for intolerable grade 2 or grade 3 toxicities will be at the discretion of the investigator based upon the nature of the AE and whether one drug can be clearly implicated or not; in the case that one drug can be clearly implicated, only that drug should be dose reduced in the future; in the case that the causative agent is unclear, it is recommended that interferon and rintatolimod are reduced as directed					

